- Intervention Description: The AI CAD software has the product name Lunit INSIGHT MMG, which is CE certified. The version of the product that will be initially installed for this study is 1.1.6.1 (updated with future official releases). In the regular mammography screening process at the study hospital two radiologist readers review the image. During the study, AI CAD will be used as an independent third reader of screening mammograms and make a binary decision as do the other two readers (i.e., "flag" if anything suspicious is deemed present in the image, otherwise "healthy"). The AI CAD generates a continuous "score", for which a threshold value has been defined, above which the mammogram should be considered flagged, and below which it should be considered healthy. The threshold value was determined in a historic calibration dataset, in which the cut-off point resulted in a joint sensitivity of AI plus first reader radiologist which was 2% higher than the joint sensitivity of first reader and second reader radiologist. By this method the threshold value was preset to 0.534. The threshold value would not be changed during the course of the study.

Key Inclusion and Exclusion Criteria

All women attending screening mammography at Capio S:t Göran hospital will be considered for inclusion. The ethical review authority has waived the need to obtain individual written informed consent.

- Inclusion criterion: age 40-74 years, a standard four-view mammography examination was acquired (right MLO, right CC, left MLO, left CC)

- Exclusion criteria: having a breast implant (excluded by presence of either CCID or MLOID view position; ID = implant displaced) or having undergone mastectomy (excluded by not having a complete four-view mammography).

- For detailed information on planned statistical analysis – see separate Statistical Analysis Plan (SAP).

Study Type

Type of Study: Interventional study

Study design: All examinations will be reviewed by both human readers and AI CAD. During the course of the study, all mammograms that have been flagged by any of the three (human, human, AI) readers will go to a consensus discussion. The consensus discussion consists of an oral discussion of each flagged case, is held between at least two radiologists and results in a decision for each case to "recall" or to define as "healthy" (and not recall). During the course of this study, the radiologists in the

consensus discussion will have additional access to any information contained in the radiology system that has been generated by the AI CAD.

Date of First Enrollment

Study start was planned for March 2021. The first individual was included on April 1, 2021.

Sample Size

The study should enroll study persons with a total of 55,000 screening examinations.

Recruitment Status

Recruitment is on-going since April 1, 2021, and is expected to finish in May or June 2022.

Primary Outcome(s)

Diagnosed pathology-verified breast cancer; to be followed up at three time-points: (i) screen-detected - diagnosed after being recalled at the screening examination, (ii) adding non-screen-detected cancer diagnosed within 12 months after the screening examination and (iii) adding non-screen-detected cancer diagnosed within 23 months after the screening examination, not including the following screening examination (such that all cancers diagnosed over a full screening cycle are captured).

Secondary Outcome(s)

1. Reader flagging [YES|NO], i.e., each reader (radiologist or AI) makes an assessment that there is an abnormal finding warranting the examination to continue to the consensus discussion. Radiologist id codes will be recorded.
2. Consensus recall [YES|NO], i.e., a decision by the consensus discussion to recall the woman for further work-up. Radiologist id codes will be recorded.
3. Tissue sampling [YES|NO], i.e., decision by the radiologist to perform tissue sampling after additional diagnostic imaging of a recalled woman.
4. Process failures in generating the AI score or in transferring the AI score to the appropriate datapoint in the radiological RIS/PACS system.

In addition, several additional exploratory objectives and endpoints exist; see the detailed Statistical Analysis Plan.

Ethics Review

Approved on April 28, 2020, with registration id EPM 2020-00487 by the Ethical Review Authority of Sweden (email: [contact], [contact]).

Completion date

Estimated May to June, 2022.

Summary Results

N/A

IPD sharing statement

We plan to share individual participant-level data to the extent that the data can be considered anonymous by the responsible research body. A transfer agreement for academic research purposes will be required.

SPIRIT-AI additional items

Protocol Version

1.1, April 29, 2022.

Funding

See WHO above.

Roles and responsibilities

Protocol contributors

[name] PhD, Karolinska University Hospital: Principal Investigator

The overall aim of the project is to examine how an AI CAD computer algorithm can independently assess screening mammograms, in a prospective clinical setting, in order to improve the accuracy of breast cancer screening and/or to replace radiologists.

Trial design

See WHO above, "Study Type"

Study setting

The study will be conducted in Capio S:t Görans hospital, one large breast center in Stockholm, in size it is the second of the three that cover the entire Stockholm area. They invite more than 70,000 to breast cancer screening each year. The breast imaging department has around five to seven dedicated breast radiologists. The x-ray equipment for screening mammography is from Philips and Sectra.

Eligibility criteria, Interventions, Outcomes

See WHO above

Participant timeline

Enrollment will start as soon as all IT systems have been integrated and tested, estimated to March 2021. For each participant there will be a follow-up period of 12 and 23 months for collecting information on both screen-detected cancer and interval cancer (i.e., cancer diagnosed after the current screening and before the next planned one).

Sample size

See WHO above

Recruitment

Recruitment will continue until the target of 55,000 examinations is reached

Sequence generation, allocation concealment mechanism, implementation

Not applicable. All participants will receive intervention.

Blinding

In the initial read, the first radiologist will not have access to AI CAD information. The second radiologist will be instructed to first enter his/her own decision, and then toggle on the AI CAD information. During the consensus discussion, the radiologists will have access to any available information from the AI CAD.

Data collection methods

Data from the radiology system and the AI CAD will be stored by each system and collected at the end of the study, or before any interim analysis. Data on cancer characteristics will be collected from the electronic medical records at the study hospital. Data on all cancer diagnoses will subsequently be collected through linking to the regional cancer registry when data is complete for 23-month follow-up of all study participants. All data will be linked based on the unique national personal identity number of each study person.

Data management

Data will remain stored at the study hospital during the course of the study. When required for interim or final analysis, data will be extracted for research purposes under the responsibility of the PI. This data will be stored following the usual practice in the breast imaging research group at the Karolinska University Hospital, including pseudonymization before any statistical analysis. Each data parameter will undergo type and range checks for validity. Further details on data management can be found in the Data Policy document of the breast imaging research group.

Statistical methods

See separate Statistical Analysis Plan (SAP) document.

Data monitoring

There is no data monitoring committee. This has not been deemed necessary since all continuously collected data will be automatically recorded in the radiology system and electronic medical record of the hospital.

Interim analysis can take place regarding acceptance and compliance for the AI system among medical staff at the hospital. Interim analysis can also take place regarding the frequency of initial reads flagged by AI CAD and flagged by radiologists. Interim analysis will not aim to assess the

accuracy of the AI CAD (in order not to influence the level of trust that radiologists put in the AI CAD assessments).

Harms

The intervention is a computer-based processing of mammography images that are acquired according to usual practice, which means no additional harm is possible.

Auditing

No auditing is planned.

Research ethics approval

See WHO above.

Protocol Amendments

Any protocol amendment will be decided by the Steering Committee. If the amendment is deemed to require additional permission by the Ethical Review Authority this will be sought before communication. Then, the amendment will be communicated to the Steering Committee and the Funder, as well as included in the updated study protocol.

Consent or ascent

Not applicable. The Ethics Review Authority has waived the need for individual written informed consent.

Confidentiality

All personal information will be handled according to GDPR and other applicable laws. Data will be pseudonymized before statistical analysis is performed. Pseudonymized data may be made available to the Funder for auditing.

Declaration of interests

The Funder (Lunit Inc.) funds the study through cost-based compensation agreed directly with Capio S:t Görans hospital, and by allowing use of the study device (AI CAD) free of charge. Outside this study, the principal investigator receives fees from the funder for conducting presentations of his work. The principal investigator is entitled to regular salary for work hours from the sponsor hospitals.

Access to data

The final trial dataset will be available for the research team of the principal investigator. Pseudonymized data can be made available for external research audit. Anonymous data may be shared with academic researchers.

Ancillary and post-trial care

Not applicable. Patients are always covered by the national Swedish patient insurance.

Dissemination policy

Investigators plan to communicate findings primarily through original research papers and through participation in professional meetings. In addition, the investigators will communicate with the general public through media and through presentations at patient association gatherings. For research papers, the inclusion of co-authors will follow ICMJE recommendations. We do not intend to use professional writers outside the investigator team. While access may be granted to academic researchers, public access to complete participant-level data will not necessarily be granted. The statistical code may be shared publicly.

Appendices

None.

Figure 1. The actual work flow in the study. If any one of the initial readers (First Radiologist, Second Radiologist or AI) decides to flag for a suspicious finding in the image, the exam is routed to the consensus discussion. The consensus discussion consists of an oral discussion between at least two radiologists (could be same or different as the initial readers) while reviewing the images of each case, and deciding to recall the woman for further diagnostics or to determine that she is healthy.

[figure not shown]
[figure not shown]

Figure 2. Alternative scenarios for which outcomes will be analyzed. The alternative at the top of each column is the actual implementation in the study. However, based on the recorded assessments of each radiologist and AI, other alternative scenarios will be analyzed in post-study analysis.

STATISTICAL ANALYSIS PLAN (SAP)

DOCUMENT UPLOADED FOR STUDY REGISTRATION

Official Title: Artificial Intelligence in a Population-based Breast Cancer Screening - the Prospective Clinical Trial ScreenTrust CAD

Unique Protocol ID: STGKS001

NCT ID: NCT04778670

Document Date: April 25, 2022

Approvals

ScreenTrust CAD Analysis Plan

Authors	[name], PI
	[name], study statistician

Approvals

ScreenTrust CAD Analysis Plan

Authors	[name], PI
	[name], study statistician

Revision history

Version	Date	Changes after study start
1.2	May 16, 2022	Added clarification of secondary analyses (4.1 and 5.0) and analyses relying on true and false negatives (5.0, 5.5, and Table 1).
1.1	Apr 29, 2022	Added brief publication plan (1), updated study population definition to be identical to research protocol (3.1), added the numeric value of the abnormality threshold (5.3), added methods to handle and minimize missing data (5.9).
0.9	Feb 22, 2021	Version before study start
0.3	Dec 22, 2020	Draft

1 Preface

This Statistical Analysis Plan (SAP) describes the planned analyses for

Image analysis with artificial intelligence to increase precision in breast cancer screening, the ScreenTrust CAD substudy, a prospective trial of AI as an independent reader of screening mammograms ("ScreenTrust CAD")

Study has been registered at clinicaltrials.gov: 04778670

The planned analyses identified in this SAP will be included in future manuscripts. Exploratory analyses not necessarily identified in this SAP may be performed to support planned analyses. Any post-hoc exploratory or unplanned analyses not specified in this SAP before database lock will be identified as such in manuscripts for publication, and added as amendments to this SAP.

This SAP was written by statistician and principal investigator who were blinded to any assessments already performed by AI or human radiologists, and to outcomes.

The first manuscript for publication after inclusion ends, will focus on the primary endpoint of the study and a screen-positive outcome. Later publication will focus on secondary endpoints and on the primary endpoint at follow-up time 12 months and 23 months after the initial screening.

2 Background

Breast cancer is the most common cancer for women. Though the patients have a relatively good probability of survival, around 1500 women die each year in Sweden from the disease. Mammographic screening has been shown to lower mortality by around 30% (1). However, in breast cancer screening programs large resources are consumed and around 30 percent of cancers go undetected and the women find them by noticing a lump in her breast (2, 3). One method to increase the accuracy of screening has been through double-reading whereby two radiologists assess all images (4). This increases accuracy, at the cost of requiring more radiologists.

Over the last years, an increasing number of scientific articles have described successful attempts in using deep learning for mammographic tumor detection and lately also for prediction of future breast cancer and workflow management (5-7). Lately, we have evaluated how three different commercially available AI algorithms would perform as independent readers of screening mammograms within a retrospective cohort from Karolinska University Hospital (8). We found that one algorithm had a sensitivity of 81.9% (95%CI: 78.9 to 84.6%) which was markedly better than the second-best algorithm (sensitivity 67.4%; 95%CI: 63.9 to 70.8%). It was also better than the first-reader radiologist (sensitivity 77.4%; 95% CI: 74.2 to 80.4%). Positive follow-up findings were determined by pathology-verified diagnosis at screening or within 12 months thereafter. The current planned study will further determine how well the AI algorithm performs in a prospective population-based screening setting.

3 Design

This is a prospective clinical trial following a paired screen-positive design (9), with the aims to assess the performance of an AI algorithm combined with radiologists(s) compared to standard-of-care being two radiologists assessing screening mammograms in a true screening population (Figure 1). The study has paired design. All examinations will receive a flagging decision by: first reader, second reader, and AI. The first reader will not have access to AI. The second reader will first record her/his decision, then review AI to make a joint decision (forced to be flagged if the second reader and/or AI made a flagging decision). In the consensus discussion, two or more radiologists will discuss all flagged cases, having access to AI information. Since all decisions by individual readers will be recorded, it is possible to determine what the outcome would have been had one or two of the readers not been allowed to assess images, and to determine what the outcome would have been had the recall decision been performed by consensus decision (actual) compared to single reader arbitration of discordant cases (Figure 2).

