4.1 Primary endpoint

Diagnosed pathology-verified breast cancer; to be followed up at three time-points: (i) screen-detected - diagnosed after being recalled at the screening examination, (ii) adding non-screen-detected cancer diagnosed within 12 months after the screening examination and (iii) adding non-screen-detected cancer diagnosed within 23 months after the screening examination, not including the following screening examination (such that all cancers diagnosed over a full screening cycle are captured).

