All analysis will take place after the relevant end-point(s) has been measured for all study persons. To be explicit, the **fourth explorative objective** above does not require any end-points in terms of cancer detection, but concerns the radiologists' behavior in the consensus discussion and specifically their adherence to the AI decisions. Since it will provide no information on whether the AI system performs well or not, the analysis can be performed before the inclusion has ended.

Analysis based on screen-detected cancer as ground truth will be performed at the earliest 1 month after the mammogram of the last included study person has been acquired and the first version of the database has been released (Figure 3). Analyses including clinical cases will be performed according to the definition of the primary end-point following the release of the database in its second and third version respectively. All statistics, including tables, figures and listings, will be performed using Stata version ≥ 16 or R version ≥ 4.0 .

The data structure in the study will have the following outline (where the endpoint=negative 2x2 table will be constructed for each stage of radiological assessments: 1. Reader flagging; 2. Consensus discussion; 3. Tissue sampling (biopsy)):

	Endpoint = positive (yes)		Endpoint = negative (no)	
	SOC positive	SOC negative	SOC positive	SOC negative
Positive using novel reader combination including AI positive	a	b	e	f
Negative using novel reader combination including AI negative	c	[d]	g	[h]

Here, SOC denotes standard of care (defined as two human radiologists). The SOC can then be compared with respect to number of endpoint positive (cancers detected) and endpoint negative (no cancer detected) with novel reader combinations including AI (Figure 2).

It should be noted that since only patients who screen positive on either SOC or SOC together with AI are referred for further work-up, the number of patients reported between brackets are unknown. This is a feature of the screen-positive design and means that absolute sensitivity and specificity cannot be estimated.

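### Recorded reads show what each reader combination would have flagged, but recall and cancer verification come from a consensus that saw AI output, so the primary rTPF can be biased in either direction

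*Combined protocol and SAP*

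**What the plan says.** SAP section 3 (Design) states that, since individual decisions are recorded, "it is possible to determine what the outcome would have been had one or two of the readers not been allowed to assess images". The same paragraph describes the consensus step: "two or more radiologists will discuss all flagged cases, having access to AI information". The protocol agrees under Blinding: "During the consensus discussion, the radiologists will have access to any available information from the AI CAD". Neither document describes a consensus held without AI output.

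The protocol's study design and Figure 1 leave the choice between recall and no recall to the consensus. SAP 4.1 defines the first time-point as "i) screen-detected - diagnosed after being recalled at the screening examination".

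On the second reader, SAP section 3 says: "The second reader will first record her/his decision, then review AI to make a joint decision". The flagging decision of two unaided radiologists is therefore on record.

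SAP 5.4 makes the primary analysis a comparison of initial-read flagging: AI plus first reader against first plus second reader, by rTPF. The note under the 2×2 table in SAP section 5 says that "only patients who screen positive on either SOC or SOC together with AI are referred for further work-up", and it treats only the bracketed cells, d and h, as unknown. SAP section 5 also plans a relative false positive fraction (rFPF) against SOC at three stages: flagging, consensus and biopsy.

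**The concern.** A flag does not by itself establish whether a woman has cancer. A flagged woman is worked up only if the consensus recalls her, and the consensus can see whether AI flagged her. In the primary comparison the two discordant cells are narrow:

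- Cell c holds cancers flagged by the second reader only (first reader and AI both negative).
- Cell b holds cancers flagged by AI only.

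Both kinds of examination go to a consensus that knows the AI result. A cancer dismissed there is absent from its cell at the first time-point, and the estimate (a+b)/(a+c) moves. SAP 5.4 and 5.7 power the study on this time-point, and the Preface assigns it to the first manuscript. At stake are the reported rTPF and the true error rate of the non-inferiority test.

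A second consequence does not depend on the size of any bias. SAP section 5 defines SOC as two human radiologists, but the observed consensus and biopsy decisions all follow disclosure of the AI result. The stage 2 and 3 rFPF therefore does not compare with ordinary two-radiologist practice.

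**Working it through.** **Inputs.** From SAP 5.7: 55,000 women, prevalence 0.5%, TPF 0.70 (taken as TPF_SOC), planning rTPF 1.02, margin 0.85, one-sided alpha 0.025. Expected cancers: 55,000 × 0.005 = 275. The joint detection probability J of the two reader combinations is not stated.

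**The plan's power figure.** Power = Φ(ln(1.02/0.85)/√V − 1.96), with V = [(1 + 1.02) × 0.70 − 2J]/(275 × 1.02 × 0.70²). This gives 79.7% at the lowest feasible J (0.414), 87.0% at J = 0.467 and 91.3% under independence (0.4998). The stated 87% is attainable but depends on an unstated J. That is a separate matter and does not affect this point.

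**Cells.** With g = rTPF: a = 275J, b = 275(0.70g − J), c = 275(0.70 − J). J is set by a correlation ρ between the combinations, J = p₁p₂ + ρ√[p₁(1−p₁)p₂(1−p₂)], with p₁ = 0.70 and p₂ = 0.70g. I assume ρ from 0 to 0.7.

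**Dismissal.** Let v_b and v_c be the verified proportions of cells b and c relative to cell a. Then:

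- observed rTPF = (a + b·v_b)/(a + c·v_c)
- SE = √[(b+c)/((a+b)(a+c))], the SAP's formula, applied to the cells after loss
- P(claim non-inferiority) = Φ(ln(observed rTPF/0.85)/SE − 1.96)

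**Results at true rTPF 0.85,** where the error should be 2.5%. At ρ = 0 the cells are a = 114.5, b = 49.1, c = 78.0. At ρ = 0.7 they are 157.8, 5.8 and 34.7.

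| Loss | Observed rTPF, ρ = 0 | Error, ρ = 0 | Observed rTPF, ρ = 0.7 | Error, ρ = 0.7 |
|---|---|---|---|---|
| None | 0.850 | 2.5% | 0.850 | 2.5% |
| 10% of c only | 0.886 | 9.7% | 0.866 | 7.6% |
| 10% of b only | 0.825 | 0.7% | 0.847 | 2.0% |
| 10% of both | 0.859 | 3.7% | 0.862 | 6.2% |

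Example (ρ = 0, 10% of c lost): (114.5 + 49.1)/(114.5 + 70.2) = 0.886 and SE = 0.0628. So ln(0.886/0.85)/0.0628 − 1.96 ≈ −1.30, a probability of about 9.7%.

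At the lowest feasible J for rTPF 0.85 (0.70 + 0.595 − 1 = 0.295), the three loss scenarios give 11.5%, 0.4% and 3.1%.

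**Tipping count at an observed rTPF of 1.02,** with none lost from b. Find the smallest x for which cells (a, b, c + x) give a lower 95% limit at or below 0.85.

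- ρ = 0: a = 137.4, b = 58.9, c = 55.1, so x = 15. This is 15/(55.1 + 15) = 21% of all second-reader-only cancers.
- ρ = 0.7: a = 177.3, b = 19.0, c = 15.2, so x = 23. This is 23/(15.2 + 23) = 60%.

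**The case against.** The strongest objection is that the primary comparison concerns flagging, and flagging is observed. The first reader has no AI access, and the second reader records a decision before seeing AI. That stands, so it would be wrong to say that the SOC read itself is unobserved. But rTPF counts flagged cancers, and at the first time-point cancer status is reached only through recall.

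A reader might infer that the design tilts the test in AI's favour, because AI-negative second-reader flags can be dismissed. The documents do not support a fixed direction. AI-only flags pass the same consensus without support from either initial reader, and SAP 5.6.7 itself anticipates examinations flagged by AI alone and not recalled. Losing those cancers works against AI.

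Nor does the tipping count show a fragile result at the planning assumption. It requires 21-60% of second-reader-only cancers to be dismissed with none lost from b. A consensus without AI would also dismiss some second-reader-only flags, so not all such loss can be put down to AI.

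The SAP already covers part of this. SAP 4.1, 5.4 and Table 1 together place flagged cancers found later in cells a, b and c at 12 and 23 months. SAP 5.6.9 examines consensus errors by flag pattern, and the fourth exploratory objective studies how far AI information is taken into account. However, follow-up recovers only cancers that surface clinically in the window, 5.6.9 is exploratory, and none of the sensitivity analyses 5.5.1 to 5.5.3 deals with dismissed examinations. The screen-detected primary test in the first manuscript remains uncorrected.

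**Conclusion.** The gap is structural and follows from the documents' own text. The statement in SAP section 3 is true for initial-read flagging. It is not true for what a consensus without AI would have recalled, or for which cancers would then have been verified. The note in SAP section 5 is incomplete, because at the first time-point cells a, b and c also lack cancers from flagged but dismissed examinations. SOC in the stage 2 and 3 rFPF is an AI-informed consensus.

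The bias in the primary rTPF can run either way. Loss from c favours AI, loss from b works against it, and equal proportional loss from both pulls rTPF towards 1, which helps a non-inferiority claim when the true value is below 1. In the illustration, a 10% loss moves the nominal 2.5% error to between 0.7% and 9.7%, depending on the cell. These sizes rest on assumed loss rates relative to cell a and an assumed correlation of 0 to 0.7. The documents give neither, so the figures show what is possible and do not estimate what occurred.

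**What to change.** 1. In SAP section 3, limit the statement to initial-read flagging. In SAP section 5, correct the note so that flagged but dismissed examinations are also described as unverified. Label the stage 2 and 3 results as given an AI-informed consensus.
2. Add to SAP 5.5 a two-way tipping-point analysis of the screen-detected primary test. Recompute rTPF and its lower limit for (a, b + x_b, c + x_c) over a grid of undetected cancers among dismissed AI-only (x_b) and dismissed second-reader-only (x_c) examinations, and mark where the limit crosses 0.85. Show beside it the numbers flagged, recalled and dismissed for each flag pattern, which bound x_b and x_c.
3. At 12 and 23 months, report by flag pattern how many of the added cancers came from flagged but dismissed examinations.

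The cost is a few extra tables from data already recorded or already planned for collection, and a narrower claim. The workflow does not change.
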